7. RESEARCH QUESTION AND OBJECTIVES

Research Question:

In this study, different from other studies in the literature, the data will be collected to observe the quality of life and efficacy after first line interferon alpha and second line TKI treatments.

Primary Objective:

- Measurement of health-related quality of life with targeted therapy used as 3rd line.
- Overall response rate at the end of follow up
- Median progression free survival according to RECIST version 1.1

Secondary Objectives:

- Overall survival rate
- Effect of quality of life on prognosis.
- Adverse events during 3rd line targeted treatment according to CTCAE.4.03
- Dose modifications due to adverse events
- Correlation between efficacy (overall response rate at month 12 and median PFS) and dose modifications due to adverse events
- Correlation between efficacy (overall response rate at month 12 and median PFS) and blood pressure

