8.7. Data analysis

Statistical analyses will be primarily of explorative and descriptive nature. All issues concerning patient validity, data consistency checks, permissible data modifications will be described in detail in the Data Management Plan.

Patients who took at least one dose of 3rd line treatment and have sufficient information whether they had an adverse event or not will be valid for safety analysis. Patients who took at least one dose of 3rd line treatment and have any information regarding efficacy of 3rd line treatment will be valid for intent-to-treat efficacy analysis.

Demographic data, baseline characteristics, diagnosis and prior treatment of RCC, concomitant diseases, and concomitant medication will be described with summary statistics such as mean, SD, minimum, 1, 5, 25, 75, 95, 99 percent quartiles, median, maximum for continuous variables, and category counts and frequencies (percentages) for

categorical variables. Concomitant diseases on the case report form correspond to MedDRA terms. Concomitant medication will be coded using WHO's drug dictionary.

Descriptive summaries of Kaplan-Meier (KM) estimates (including number of failed, number censored, 25th and 75th percentiles with respective 95% confidence level and median with 95% confidence level) and KM curves will be presented for time-to-event efficacy variables (PFS, TTP, time to treatment failure). Mean, SD, minimum, 1, 5, 25, 75, 95, 99 percent quartiles, median, maximum will be produced for duration of TKI treatment. Category counts and frequencies (percentages) will be calculated for tumor status at different visits and general subjective rating of efficacy of TKI from the treating physician.

Adverse events will be summarized using the MedDRA and the CTCAE coding system. Event rates for single adverse events will be calculated based on the total number of patients valid for safety. Adverse events will be categorized according to relation, seriousness, CTCAE grade (version 4.03), and discontinuation of therapy, action taken and outcome. Serious adverse events and unexpected or unlisted ADRs will be evaluated separately.

Category counts and frequencies (percentages) will be calculated for overall tolerability.

The factors, which might have impacted the duration of treatment, will be studied by retrospectively.

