10. MANAGEMENT AND REPORTING OF ADVERSE EVENTS/ADVERSE REACTIONS

Safety event	Recorded on the case report form	Reported on the NIS AEM Report Form to Pfizer Safety within 24 hours of awareness
SAE	All	All
Non-serious AE	All	None
Scenarios involving exposure to a drug under study, including exposure during pregnancy, exposure during breast feeding, medication error, overdose, misuse, extravasation; lack of efficacy; and occupational exposure	All (regardless of whether associated with an AE), except occupational exposure	All (regardless of whether associated with an AE)

For each AE, the investigator must pursue and obtain information adequate both to determine the outcome of the adverse event and to assess whether it meets the criteria for classification as a SAE (see section "Serious Adverse Events" below)

Safety events listed in the table above must be reported to Pfizer within 24 hours of awareness of the event by the investigator **regardless of whether the event is determined by the investigator to be related to a drug under study**. In particular, if the SAE is fatal or life-threatening, notification to Pfizer must be made immediately, irrespective of the extent

of available event information. This timeframe also applies to additional new (follow-up) information on previously forwarded safety event reports. In the rare situation that the investigator does not become immediately aware of the occurrence of a safety event, the investigator must report the event within 24 hours after learning of it and document the time of his/her first awareness of the events.

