An investigator's causality assessment is the determination of whether there exists a reasonable possibility that 3rd line treatment caused or contributed to an adverse event. If the investigator's final determination of causality is "unknown" and s/he cannot determine whether 3rd line treatment caused the event, the safety event must be reported within 24 hours.

If the investigator cannot determine the etiology of the event but s/he determines that *3rd line treatment* did not cause the event, this should be clearly documented on the case report form and the NIS AEM Report Form.

DEFINITIONS OF SAFETY EVENTS

Adverse events

An AE is any untoward medical occurrence in a patient administered a medicinal product. The event need not necessarily have a causal relationship with the product treatment or usage. Examples of adverse events include but are not limited to:

- Abnormal test findings (see below for circumstances in which an abnormal test finding constitutes an adverse event);
- Clinically significant symptoms and signs;
- Changes in physical examination findings;
- Hypersensitivity;
- Lack of efficacy;
- Drug abuse;
- Drug dependency.

Additionally, for medicinal products, they may include the signs or symptoms resulting from:

- Drug overdose;
- Drug withdrawal;
- Drug misuse;
- Off-label use;
- Drug interactions;
- Extravasation;
- Exposure during pregnancy;
- Exposure during breast feeding;
- Medication error;

- Occupational exposure.

Abnormal test findings

The criteria for determining whether an abnormal objective test finding should be reported as an adverse event are as follows:

- Test result is associated with accompanying symptoms, and/or
- Test result requires additional diagnostic testing or medical/surgical intervention, and/or
- Test result leads to a change in study dosing or discontinuation from the study, significant additional concomitant drug treatment, or other therapy, and/or
- Test result is considered to be an adverse event by the investigator or sponsor.

Merely repeating an abnormal test, in the absence of any of the above conditions, does not constitute an adverse event. Any abnormal test result that is determined to be an error does not require reporting as an adverse event.

Serious adverse events

A serious adverse event is any untoward medical occurrence in a patient administered a medicinal or nutritional product (including pediatric formulas) at any dose that:

- Results in death;
- Is life-threatening;

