- Requires inpatient hospitalization or prolongation of hospitalization (see below for circumstances that do not constitute adverse events);
- Results in persistent or significant disability/incapacity (substantial disruption of the ability to conduct normal life functions);
- Results in congenital anomaly/birth defect.

Progression of the malignancy under study (including signs and symptoms of progression) should not be reported as a serious adverse event unless the outcome is fatal within the safety reporting period. Hospitalization due to signs and symptoms of disease progression should not be reported as a serious adverse event. If the malignancy has a fatal outcome during the study or within the safety reporting period, then the event leading to death must be recorded as an adverse event and as a serious adverse event with severity Grade 5.

Medical and scientific judgment is exercised in determining whether an event is an important medical event. An important medical event may not be immediately life-threatening and/or result in death or hospitalization. However, if it is determined that the event may jeopardize the patient or may require intervention to prevent one of the other outcomes listed in the definition above, the important medical event should be reported as serious.

Examples of such events are intensive treatment in an emergency room or at home for allergic bronchospasm; blood dyscrasias or convulsions that do not result in hospitalization; or development of drug dependency or drug abuse.

Additionally, any suspected transmission via a Pfizer product of an infectious agent, pathogenic or non-pathogenic, is considered serious. The event may be suspected from clinical symptoms or laboratory findings indicating an infection in a patient exposed to a Pfizer product. The terms “suspected transmission” and “transmission” are considered synonymous. These cases are considered unexpected and handled as serious expedited cases by PV personnel. Such cases are also considered for reporting as product defects, if appropriate.

Hospitalization

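### Treatment changes made because the tumour progressed can be recorded as dose modifications for adverse events, and can bias that variable's correlation with response and PFS

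*Combined protocol and SAP*

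**What the plan says.** Section 10 defines an AE broadly. On causality it says: "The event need not necessarily have a causal relationship with the product treatment or usage". Its list of examples includes "Lack of efficacy". Under the sub-heading on abnormal test findings, one criterion for reporting a finding as an AE is "Test result leads to a change in study dosing or discontinuation from the study"; imaging that shows progression is not excepted.

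Under the sub-heading on serious adverse events: "Progression of the malignancy under study (including signs and symptoms of progression) should not be reported as a serious adverse event". The one exception is a death that falls inside the reporting window. If the malignancy is fatal, the event leading to death is recorded both as an AE and as a Grade 5 serious AE. There is no matching sentence for non-serious AEs, and the table that opens section 10 sends all of those to the case report form.

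The same table has a separate row of exposure scenarios, ending in "medication error, overdose, misuse, extravasation; lack of efficacy; and occupational exposure". The instruction for the case report form in that row is "All (regardless of whether associated with an AE), except occupational exposure". The later paragraph on lack of efficacy likewise asks for a report whether or not an AE is present, but it speaks of the sponsor's products, where the table speaks of any drug under study.

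The analysis side is in two places. A secondary objective in section 7, repeated in the abstract, is "Correlation between efficacy (overall response rate at month 12 and median PFS) and dose modifications due to adverse events". Section 8.7 says: "Adverse events will be categorized according to relation, seriousness, CTCAE grade (version 4.03), and discontinuation of therapy, action taken and outcome".

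**The concern.** The objective is of interest if it shows whether patients whose treatment is altered for toxicity do better or worse. That requires an exposure that is not itself a consequence of the outcome. If a site records progression, or the scan that shows it, as an AE and then records the resulting interruption or dose change as the action taken, the outcome has caused the exposure for that patient. Enough such entries would produce an association between modification and short PFS or non-response even when toxicity-driven changes are unrelated to efficacy.

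The same entries would enter the AE rates and the AE-related discontinuation counts of section 8.7, which would then mix toxicity with treatment failure. Unless the case report form holds a reason for each change, the two kinds may not be separable after database lock.

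**Working it through.** **Step 1. The texts side by side**

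| Place | Bearing on lack of efficacy or progression |
|---|---|
| Section 10, AE examples | Lack of efficacy is an AE |
| Section 10, abnormal test findings | A result that changes dosing is reportable as an AE |
| Section 10, serious AEs | Non-fatal progression kept out of serious AEs only; fatal malignancy is an AE and a Grade 5 serious AE |
| Section 10, table and lack-of-efficacy paragraph | Separate scenario; need not involve an AE |
| Abstract and section 8.3, variable list | Interruption, reduction and elevation, grouped with side effects; operational-definition column empty |
| Section 8.7 | AEs classified by discontinuation and action taken; no rule separates toxicity from progression |

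The route from progression to an AE-driven modification is therefore open but not prescribed. Sections 8.6 and 8.7 do not say how the correlation is to be computed.

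**Step 2. The plan's own figure**

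The only design figure used here is the sample size of 152 (section 8.5). With z = 1.96, half-width 0.076, population 1800 and p = 0.5 (assumed):

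- n0 = 1.96² × 0.25 / 0.076² = 166.3
- n = 166.3 / (1 + 165.3/1800) = 152.3

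It reproduces. The point does not depend on it; 152 only sets the scale below.

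**Step 3. How many patients could be affected**

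The protocol gives no PFS median. Assume exponential PFS with median m months, so the proportion progressing by month 12 is 1 − 2^(−12/m).

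- m = 4: 0.875, or 133 of 152
- m = 6: 0.750, or 114 of 152
- m = 9: 0.603, or 92 of 152

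These are ceilings on the number at risk of such an entry, not forecasts.

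**Step 4. Spurious odds ratio**

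Assume that 40% of patients have a toxicity-driven modification regardless of outcome (true odds ratio 1.0), and that a share q of progressors also has a progression-driven change coded to an AE. The proportion modified is 0.4 + 0.6q in progressors and 0.4 in non-progressors.

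| q | Modified, progressors | Odds ratio |
|---|---|---|
| 10% | 0.46 | (0.46/0.54)/(0.40/0.60) = 1.28 |
| 20% | 0.52 | (0.52/0.48)/(0.40/0.60) = 1.63 |
| 50% | 0.70 | (0.70/0.30)/(0.40/0.60) = 3.50 |

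This contrast is progression by month 12, a stand-in for the response rate and PFS named in the objective.

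**Step 5. Simulation on PFS itself**

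The set-up was 152 patients, 2,000 runs per setting, the three medians above, PFS cut at 12 months, and toxicity-driven modification in 30% or 50% of patients independent of PFS. The statistic was the Spearman correlation of modified (yes/no) with PFS time, tested two-sided at 5%. Section 8.6 gives 0.05 without stating sidedness. Ranges are over the medians and toxicity rates.

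| q | Mean correlation | Runs rejecting |
|---|---|---|
| 0 | about 0 | 4.6–5.9% |
| 10% | −0.02 to −0.06 | 5–12% |
| 25% | −0.05 to −0.15 | 8–46% |
| 50% | −0.10 to −0.30 | 26–96% |
| 100% | −0.38 to −0.67 | 100% |

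The bias is always towards modified patients having shorter PFS. It is small at q of about 10% and vanishes at q = 0.

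**The case against.** A reader might infer that the plan requires progression-driven changes to be counted as AE-driven modifications, and that the correlation is therefore circular. The documents do not go that far, for these reasons:

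- No sentence says that such changes count. The abstract and section 8.3 group the variable with side effects, which points to toxicity. This stands, although dose elevation is in the same list and is hard to read purely as a response to toxicity.
- Section 10 twice handles lack of efficacy as something that need not be an AE. This stands as evidence of a conflict. It does not cancel the AE list, so sites can reasonably code either way.
- Lack of efficacy is never equated with RECIST progression, and the rule for fatal malignancy suggests that non-fatal progression is not automatically an AE. This stands as a fair reading. The test-finding criterion still leaves a second route.
- Permanent discontinuation is not among the listed modifications; section 8.3 makes it a failure event for time to treatment failure. This stands for the correlation. Discontinuation remains an AE category in section 8.7, so those counts are still exposed.
- The e-CRF and the Data Management Plan are not available here and may already record separate reasons. This cannot be settled from the protocol.
- The objective is secondary, section 8.5 says there is no hypothesis to test, and section 8.7 calls the analyses mainly exploratory. This limits the stakes but does not make a biased correlation easier to interpret.

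**Conclusion.** The point holds as a conflict in section 10 combined with an undefined exposure. Progression-driven interruptions and dose changes can enter the AE-driven modification variable, making its correlation with response and PFS partly circular and biased in the negative direction. They can also inflate AE and AE-related discontinuation rates. Full circularity would need nearly all progressors to be coded this way, and nothing in the documents says they would be.

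The size is unknown because q is unknown. The odds ratios of about 1.3, 1.6 and 3.5 rest on the assumed 40% toxicity rate and on q of 10%, 20% and 50%; the simulation rests on assumed medians and toxicity rates. The sample size and the primary objectives are not affected.

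**What to change.** 1. In section 10, reconcile the AE examples, the test-finding criterion, the serious-AE exemption, the table and the lack-of-efficacy paragraph on whether lack of efficacy or progression is an AE. Leave safety reporting to the sponsor unchanged.
2. In sections 7 and 8.7, define the exposure as interruptions, reductions or elevations whose recorded reason is an AE other than lack of efficacy or progression, dated before progression. Confirm that the e-CRF captures the reason and the date.
3. In section 8.7, show lack-of-efficacy and non-fatal progression entries on a separate line from the toxicity AE rates. Keep the fatal Grade 5 events in the AE and serious-AE tables, as section 10 requires. Leaving all progression out of those tables would contradict that rule.

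The cost is a few sentences and a filter on a reason field. AE counts will be split over two displays and must be reconciled with the safety database. The date rule does not address one separate matter: patients who stay progression-free longer have more time in which to have a dose change. The analysis text should say how follow-up time is handled, for example by a time-dependent exposure or a landmark.

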10.1. Single reference safety document

The local product label information highlighted in the appendix 3 will serve as the single reference safety document during the course of the study, which will be used by Pfizer safety to assess any safety events reported to Pfizer Safety by the investigator during the course of this study.

The SRSD should be used by the investigator for prescribing purposes and guidance.

11. PLANS FOR DISSEMINATING AND COMMUNICATING STUDY RESULTS

Not applicable

COMMUNICATION OF ISSUES

In the event of any prohibition or restriction imposed (e.g., clinical hold) by an applicable Competent Authority in any area of the world, or if the investigator is aware of any new information which might influence the evaluation of the benefits and risks of a Pfizer product, Pfizer should be informed immediately.

In addition, the investigator will inform Pfizer immediately of any urgent safety measures taken by the investigator to protect the study patients against any immediate hazard, and of any serious breaches of this NI study protocol that the investigator becomes aware of.

13. LIST OF TABLES

Not applicable

14. LIST OF FIGURES

Not applicable

ANNEX 1. LIST OF STAND ALONE DOCUMENTS

FKSI-15

EQ5D-3L

FKSI-DRS

Blood Pressure Diary

ANNEX 2. ENCEPP CHECKLIST FOR STUDY PROTOCOLS

Not applicable

ANNEX 3. ADDITIONAL INFORMATION

Inlyta 1 mg product label for Turkey

Inlyta 5 mg product label for Turkey

Afinitor 5 mg product label for Turkey

Afinitor 10 mg product label for Turkey

Nexavar 200 mg product label for Turkey

Sutent 12,5 mg product label for Turkey

Sutent 25 mg product label for Turkey

Sutent 37,5 mg product label for Turkey

Sutent 50 mg product label for Turkey

Votrient 200 mg product label for Turkey

Votrient 400 mg product label for Turkey

Votrient 800 mg product label for Turkey

Torisel 25 mg/ml i.v. product label for Turkey
